--------------------------------	--

	
trial. If response at 12 weeks is not recorded for the patient then the patient will be considered a non-responder.

--	--

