**5.2.1.4 Hepatic:**

Rule out non-inflammatory causes. If non-inflammatory cause, treat accordingly and continue protocol therapy. Consider imaging for obstruction.

Grade of Liver Test Elevation (NCI CTCAE v4)	Management	Follow-up
Grade 1 AST or ALT >ULN to 3x ULN and/or total bilirubin >ULN to 1.5x ULN	
 
Continue nivolumab
 
	
 
Continue liver function test monitoring per protocol
 
If worsening, treat as grade 2,3, or 4
 

Grade 2 AST or ALT >ULN to 3-5x ULN and/or total bilirubin >ULN to 1.5-3x ULN	
 
Delay nivolumab
 
Administer corticosteroids at a dose of 1-2mg/kg/day prednisone
 
	
 
Resume nivolumab and IL-2 if returns to baseline
 
If persists >5-7 days or worsens, treat as grade 3 or 4
 

Grade 3 or 4 AST or ALT >5x ULN and/or total bilirubin >3x ULN
	
 
• Discontinue nivolumab
 
• Increase frequency of monitoring to every 1-2 days
 
• 1-2mg/kg/day methylprednisolone IV or IV equivalent for grade 3 and 2 mg/kg/day methylprednisolone IV for grade 4
 
• Add prophylactic antibiotics for opportunistic infections like PCP
 
• Consult gastroenterologist
 
	
 
• If improves to grade 2, taper steroids over at least one month
 
• If does not improve within 3-5 days or worsens after improvement:             
 
○ Add mycophenolate mofetil 1g twice daily
 
○ If no response within an additional 3-5 days, consider other immunosuppressive agents per local guidelines
 
 
 

---	--	---

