**5.6 Off Protocol Specified Therapy Criteria**

Patients will be removed from protocol specified therapy when any of the criteria listed in Section 5.5 apply. The reason for ending protocol therapy and the date the patient was removed from treatment should be documented. All patients who discontinue treatment should comply with protocol specific follow-up procedures as outlined in Section 6.3. The only exception to this requirement is when a subject withdraws consent for all study procedures or loses the ability to consent freely.

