### 6.2.2 Nivolumab administration days

- Physical exam, vital signs, ECOG Performance Status, Toxicity
- Hematology: CBC with diff includes total WBC, hemoglobin, hematocrit, platelet count and differential of the WBC including absolute counts
- Serum chemistries: Comprehensive metabolic profile (COMP) includes sodium, potassium, chloride, bicarbonate, BUN, creatinine, AST, ALT, alkaline phosphatase, total bilirubin.

- Magnesium, phosphorus, LDH
- Every 12 weeks until discontinuation/completion of nivolumab on trial: TSH, free T3, free T4 (Only If Clinically Indicated: FSH, LH, ACTH).
- Whole blood will be collected for correlative analysis at certain time points. See Section 6.4 Time and Events Table including footnote #8 for the time points and the Lab Manual for collection, labeling and shipping instructions
- Blood draw for ADA (anti-drug antibody) analysis will be collected at the time points listed in Section 6.4 Time and Events Table.
- Prior to dose # 1 (subsequently ONLY if clinically indicated): 12-lead Electrocardiography
- At week 12: Echocardiogram
- Nivolumab administration will be over 60 minutes ( $\pm$  10 minutes) at a dose of 480 mg intravenously. Pre-medications or rescue medications are not specified by protocol and will be per institutional guidelines/treating investigator.
- Continue Nivolumab every 4 weeks until i) progression noted or ii) up to 48 weeks completed from start of protocol therapy (week 1) - refer to sections 5.4, 5.5. and 5.7. Nivolumab may be continued by treating investigator beyond this period off-study at his or her discretion and clinical judgment.
- Clinic visits: For patients who continue on nivolumab on trial nivolumab: every 4 weeks (from week1) with scans as in Section 6.4 Time and Events Table below.
- At week 12 and then every 12 weeks: Computed tomography of the chest, computed tomography or magnetic resonance imaging of the abdomen and pelvis, and only if clinically indicated: computed tomography or magnetic resonance imaging of the brain

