**6.3 Follow-Up Procedures**

For patients who have stopped all protocol specified therapy (IL2 and nivolumab for up to 48 weeks), follow up will be done every 12 weeks (counting from week 1) via phone or other forms of communication. In these patients, scans and/or labs will be per the treating investigator’s discretion/per standard of care and not dictated by the protocol.

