**6.4 Time and Events Table**

	Screen (<28d)	Week 1 IL2 Cycle #1	Nivolum ab Dose #1 	Week 3 IL2 Cycle #2	Nivolum ab Dose #2... 	Week 12	Subsequent 	End of treatment visit 	Follow-Up 
Informed Consent	X								
History, PE, Con Meds, Weight, Vital Signs 	X	X	X	X	X	X	X	X	X
ECOG Performance Status	X	X	X	X	X	X	X	X	
Toxicity Evaluation		X	X	X	X	X	X	X	
HD IL2 eligibility assessment	X								
Pregnancy Test for WOCBP 	X								
CBC with diff and plt 	X	X	X	X	X	X	X	X	
COMP 	X	X	X	X	X	X	X	X	
Mag, Phos, LDH	X	X	X	X	X	X	X	X	
PT/INR	X								
Urine Protein/Creatinine Ratio	X								
Urine output measurement, pulse oximetry measurement.		X (qday)		X (qday)					

	Screen (<28d)	Week 1 IL2 Cycle #1	Nivolumab Dose #1 	Week 3 IL2 Cycle #2	Nivolumab Dose #2... 	Week 12	Subsequent 	End of treatment visit 	Follow-Up 
TSH, free T3, free T4 (IF Clinically Indicated: FSH, LH, ACTH) 	X						X (q 12 weeks)	X	
Total Creatinine Kinase, Troponin T		X (day 5)		X (day 19)					
12-lead ECG	X		X				X (IF clinically indicated)		
CT chest 	X					X	X (q 12 weeks)		X 
CT or MRI abdomen/pelvis 	X					X	X (q 12 weeks)		X 
CT or MRI brain 	X					X	X 		X 
Tumor Measurements	X					X	X (q 12 weeks)		X 
Central line placement		X (day 1)		X (day 15)					
HD-Interleukin-2		X (D1-5)		X (D15-19)					
Nivolumab 			X		X	X	X... 		
Archived Tumor Tissue 	X								
Blood draw for Anti-Drug Antibody Analysis 	X		X		X	X	X (q12 weeks)		
Whole blood, 	X		X	X	X	X			
Serum 	X								
Echocardiogram 	X					X			
Study RN/Coordinator Call 		X	X	X	X	X			

**All assessments have a window of ± 3 business days except for imaging/tumor measurements where a window of ± 7 business days will apply.**

- 1: Vital signs will include temperature, pulse, respirations, blood pressure); height will be obtained at screening only.
- 2: CBC with diff includes total WBC, hemoglobin, hematocrit and differential of the WBC including absolute counts.

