- 3: Comprehensive metabolic profile includes sodium, potassium, chloride, bicarbonate, BUN, creatinine, AST, ALT, alkaline phosphatase, total bilirubin. TSH, free T3, free T4 at baseline and then repeated every 12 weeks. (IF Clinically Indicated ONLY: FSH, LH, ACTH)
- 4: With or without intravenous contrast, before or on associated visit.
- 5: Only if clinically indicated
6. Continue Nivolumab on trial every 4 weeks until i) progression noted and no clinical benefit as determined by treating investigator or ii) up to 48 weeks completed from start of protocol therapy (week 1). Please note that nivolumab could be continued by the treating investigator off-trial beyond the 48-week duration at his or her clinical discretion.
7. An archived tissue block must be **identified** with intent to submit for analysis prior to registration. See the Lab Manual for collection, labeling and shipping instructions.
- 8: Whole blood is to be collected at 5 time points: pre-all study therapy, post first HD IL2 cycle but pre-nivolumab, after the first dose of nivolumab but before the second dose of nivolumab, post second HD-IL2 cycle (before the next dose of nivolumab) and at 12 weeks on days indicated prior to study drug being administered on that day. In some patients, due to the exact timing of dose #1 of nivolumab in that patient, two of these time points might coincide and in those patients, only 4 time points will be drawn. Serum will be collected at baseline only. See the Lab Manual for collection, labeling and shipping instructions.
- 9: For patients who have stopped all protocol specified therapy, follow up will be done every 12 weeks  $\pm$  4 weeks x total of 24 months (counting from week 1) via phone or other form of communication. In those patients, scans and/or labs will be per the treating investigator's discretion/standard of care and will not be dictated by protocol.
10. WOCBP: urine or serum pregnancy test for women of child bearing potential, see section 6.1.12
11. For as long as subjects continue on nivolumab (i.e. up to 48 weeks on treatment, or beyond the 48 week duration of treatment per treating investigator's discretion): Survival status assessment at least every 12 weeks  $\pm$  4 weeks x total of 24 months (counting from week 1) with scans as noted.

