#### 11.1 Study Design/Study Endpoints/Sample Size and Accrual

For the phase 1b portion of the study: We will accrue an initial cohort of 3 patients who will be treated with sequential (rather than interspersed) treatment as follows: they will receive 2 cycles of HD-IL2 given in standard fashion (two 5-day cycles one week apart) followed by nivolumab starting the week after the second IL-2 cycle and continuing every 4 weeks as per standard nivolumab dosing. If 2 or more out of 3 of the first patients suffer a grade 3 or 4 immune related toxicity of interest (see 5.2.1) **within 28 days** from the first dose of nivolumab (**DLT period**) the study will stop. The 4th patient will not be enrolled until after the analysis of the 3 patient cohort is complete and submitted to the regulatory bodies.

If <2 patients suffer a grade 3 or 4 immune related toxicity in the cohort of 3 patients, the study will enroll 7 more patients treated with Nivolumab administered intravenously at 480 mg/dose over 60 minutes every 28 days, starting 1 to 3 weeks after the start date of the first cycle of IL2. We will monitor these patients **continuously** for immune mediated dose limiting toxicities **for 28 days** from the first dose of nivolumab (**DLT period**). Up to 10 total patients will be treated and observed for toxicity for 28 days from the first dose of Nivolumab in the phase 1b portion.

If, at any time during accrual to the phase 1 b portion, 6 patients or more have a grade 3 or 4 immune mediated event of interest (as described in section 5.2.1) we will pause the study and modify/discontinue the protocol in consultation with the site principal investigators and applicable regulatory authorities. If 5 or fewer patients experience grade 3 or 4 immune mediated toxicity of interest (see 5.2.1) during the toxicity window, then the study will continue to the phase II portion.

We choose to examine toxicity after 10 patients because if 6 patients or more are found to have a DLT then the 95% exact binomial confidence interval (26% - 88%) will be > 25% and be indicative that immune mediated toxicity with this regimen is too great.

Dose-Limiting Toxicity is defined as a grade 3 or 4 immune mediated event of interest (as listed and described in section 5.2.1). Please note: immune mediated events of interest do not include those that might occur during high dose IL-2 and are reversible.

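### PFS omits death and has no censoring rule, and the plan does not say whether a patient who permanently stops before week 12 must have the week-12 scan that decides response

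*Combined protocol and SAP*

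**What the plan says.** **PFS.** Section 7.1.6 starts PFS at the beginning of treatment and ends it at progression; death is not mentioned. Section 11.2 reports 24-month PFS and OS by Kaplan-Meier with 95% confidence intervals. No section says how patients without an event are censored.

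**Imaging.** The phase II primary endpoint is ORR at 12 weeks (Sections 11.0 and 11.2). In the Time and Events Table (6.4), the Week 12 column marks chest CT, "CT or MRI abdomen/pelvis" and tumor measurements, and footnote 9 is not attached there. Section 6.2.2, headed as nivolumab administration days, lists "At week 12 and then every 12 weeks: Computed tomography of the chest". For patients who stop, Section 5.6 says "All patients who discontinue treatment should comply with protocol specific follow-up procedures as outlined in Section 6.3". Section 6.3 says that for them "follow up will be done every 12 weeks (counting from week 1) via phone or other forms of communication". Both 6.3 and footnote 9 leave scans to the treating investigator; the footnote's words are "discretion/standard of care and will not be dictated by protocol". The end-of-treatment visit (6.2.4) lists no imaging.

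**Counting.** The synopsis states: "If response at 12 weeks is not recorded for the patient then the patient will be considered a non-responder". Section 11.1 repeats this. The synopsis, 5.9 and 11.1 define an evaluable patient by dosing: at least one dose of each drug. Section 7.1.1 additionally requires that disease was re-evaluated.

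**The concern.** A PFS endpoint that leaves out death measures something closer to time to progression. Patients who die without a documented progression would be censored or left uncounted, and the estimate labelled PFS would be too favourable. Once therapy stops, it also rests partly on scans obtained as standard of care.

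For the primary endpoint, the table points towards a scan for everyone at week 12, while 5.6, 6.3 and footnote 9 point towards discretion after therapy ends. A permanent stop before week 12 is foreseeable. Grade 3 or 4 hepatic events, for example, carry the instruction "Discontinue nivolumab", and the 28-day toxicity window closes before week 12. A responder who stopped for toxicity and was not scanned would count as a failure in a 23-patient design with almost no spare power.

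**Working it through.** **1. Reproduce the design.** Inputs from Section 11.1: null ORR 0.25, target ORR 0.46, continue if more than 2 of 12 respond, recommend further study if more than 8 of 23 respond.

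- Early stopping: P(X1 ≤ 2), with X1 ~ Bin(12, p).
- P(recommend) = Σ over x = 3 to 12 of P(X1 = x) · P(X2 ≥ 9 − x), with X2 ~ Bin(11, p).
- At p = 0.25: early stopping 39.1%, type I error 9.4%.
- At p = 0.46: early stopping 3.6%, power 80.1%.

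These agree with the stated 39%, 10% (a ceiling), 3.6% and 80%.

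**2. Is a stop before week 12 possible?** Nivolumab from week 2 plus 28 days ends about week 6. In the first three patients, who start about week 4, it ends about week 8. Both precede week 12. The phase Ib rule ("If 5 or fewer patients experience grade 3 or 4 immune mediated toxicity of interest", the study proceeds) tolerates up to 5 of 10 such events. That is a ceiling, not an expected rate, and not every such event ends treatment.

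**3. Effect of unscanned responders.** Let l be the share of true responders with no week-12 scan, all scored as non-responders. The effective rate is p(1 − l). The documents give no value for l, so these are assumptions (for instance 10% stop early × 10% unscanned = 1%; 10% × 20% = 2%; 20% × 25% = 5%).

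| l | Effective rate at 46% | Power | Early stopping at 46% | Type I error at 25% |
|---|---|---|---|---|
| 0 | 0.460 | 80.1% | 3.6% | 9.4% |
| 1% | 0.455 | 78.9% | 3.9% | 9.0% |
| 2% | 0.451 | 77.6% | 4.2% | 8.5% |
| 5% | 0.437 | 73.4% | 5.1% | 7.2% |

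Of 23 × 0.46 = 10.6 expected responders, the losses are 0.11, 0.21 and 0.53.

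**4. Effect of leaving death out of PFS.** Assume exponential event times with median m, so S(24) = 2^(−24/m). If a share d of the event hazard is death without documented progression and those deaths are censored, Kaplan-Meier estimates S(24)^(1 − d). The 4.6-month median is the nivolumab figure cited in Section 1.2; the 9-month median and all values of d are assumptions.

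| Median | d = 0 | d = 5% | d = 10% | d = 20% |
|---|---|---|---|---|
| 4.6 months | 2.7% | 3.2% | 3.9% | 5.5% |
| 9 months | 16% | 17% | 19% | 23% |

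The direction does not depend on the assumptions: for any d > 0, S^(1 − d) exceeds S.

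**The case against.** **The scan may already be required.** The Week 12 column is unconditional, and footnote 9 belongs only to Follow-Up. Where Section 6.2.2 limits an assessment to patients still on nivolumab, as for thyroid tests and clinic visits, it says so; the scan bullet has no such limit. This has real weight. A reader might infer that the protocol waives the scan for early stoppers, and the documents do not go that far. They leave the case open, since the same column also lists nivolumab and 5.6 sends every patient who stops to 6.3.

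**The power loss is assumed.** This stands. No rate of early stopping or of missing scans is given, and standard-of-care scans may fill the gap. A reader might take 5 of 10 as a discontinuation rate, but it is only a go/no-go limit. Scoring missing as non-response is also prespecified and protects type I error. Patients whose nivolumab is only on hold are not affected.

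**Evaluability.** A reader might infer that 7.1.1 would shrink the denominator, giving for instance 8/22 rather than 8/23. The documents do not support that. The synopsis and 5.9 replace non-evaluable patients, with up to 28 registrations to reach 23, and 11.1 keeps the unscanned patient as a non-responder. What remains is a wording mismatch in 7.1.1.

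**Footnotes 9 and 11.** They may look contradictory for nivolumab beyond week 48. They can be read together: footnote 11 refers to scans as marked, the Follow-Up marks carry footnote 9, and nivolumab after week 48 is off-study.

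**PFS is secondary and descriptive.** True; it does not enter the go/no-go decision. The curves above are only illustrative. Section 1.2 reports 11% progression-free at 3 years on HD IL-2, whereas the exponential curves give 0.4% (4.6-month median) and 6% (9-month median) at 36 months. At 16% with n = 23, the approximate 95% half-width, 1.96·√(0.16 × 0.84/23), is about 15 points, larger than the shifts shown. None of this makes the event definition correct. The note in 7.1.4.3 about documenting progression after discontinuation covers only symptomatic deterioration and schedules no scan.

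**Conclusion.** Three points hold, in descending order of certainty.

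- **PFS is wrong as written.** Death is not an event and there is no censoring rule, so 24-month PFS would be biased upward whenever a patient dies without documented progression. In the 9-month illustration the shift is about 1 to 7 percentage points; in the 4.6-month one, about 0.5 to 3. Death share, 9-month median and curve shape are assumptions.
- **The week-12 scan after an early permanent stop is unsettled.** If responders go unscanned, ORR is biased downward and power falls by about 1 to 7 points for assumed losses of 1% to 5%. The actual loss is unknown and could be nil. Type I error is not inflated, and sample size and decision rule need no change.
- **Section 7.1.1 differs from the synopsis, 5.9 and 11.1 on evaluability.** This is minor, because the statistical section is explicit about the primary analysis.

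**What to change.** 1. In 7.1.6 and 11.2, define a PFS event as progression or death from any cause. Censor patients without an event at the last adequate tumor assessment. Note that PFS after therapy stops rests partly on standard-of-care scans. This is a text change with no added procedure.
2. In 6.3 and footnote 9, state that the scheduled week-12 tumor assessment is done in every patient who received both drugs, on or off therapy, unless progression is already documented or consent is withdrawn. The cost is one already scheduled scan visit for the few patients off therapy by then.
3. Align 7.1.1 with the dosing-based definition and the non-responder rule, and report how many patients were scored non-responder for want of a scan. This is a text change and one line in the report.

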## 7.0 MEASUREMENT OF EFFECT

### 7.1 Antitumor Effect- Solid Tumors

Response and progression will be evaluated in this study using the new international criteria proposed by the Response Evaluation Criteria in Solid Tumors (RECIST) Committee [JNCI 92(3):205-216, 2000]. Changes in only the largest diameter (unidimensional measurement) of the tumor lesions are used in the RECIST v1.1 criteria.

#### 7.1.1 Definitions

Evaluable for toxicity. All patients will be evaluable for toxicity from the time of their first treatment with study drug.

Evaluable for objective response. Only those patients who have measurable disease present at baseline, have received at least 1 dose of HD IL2 and at least 1 dose of nivolumab, and have had their disease re-evaluated will be considered evaluable for response. These patients will have their response classified according to the definitions stated below. (Note: Patients who exhibit objective disease progression prior to the end of cycle 1 will also be considered evaluable.)

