
Study Duration	
24 months of accrual
 
24 months of follow-up (counting from week 1)

Study Center(s)	
4 Sites including lead site: University of Michigan.

Objectives	
Phase Ib:
 
Primary Objective:
 
 
1. To estimate the safety and toxicities of High Dose Interleukin-2 in combination with the immune checkpoint inhibitor Nivolumab in metastatic clear cell renal cell carcinoma.
 
 
Phase II:
 
Primary Objective:
 
 
1. To estimate the efficacy of High Dose Interleukin-2 in combination with the immune checkpoint inhibitor Nivolumab in metastatic clear cell renal cell carcinoma.
 
 
Secondary Objectives:
 
 
1. To determine the safety of High Dose Interleukin-2 in combination with Nivolumab in metastatic clear cell renal cell carcinoma.
 
2. To profile circulating T cell repertoire by flow cytometry before and during therapy.
 
 
Exploratory Objectives:
 
 
1. To bank tissue and serum specimens for correlative analyses and anti-drug antibody testing in the future.
 

Number of Subjects	
Number of evaluable subjects (those who receive at least 1 dose of HD IL2 and at least 1 dose of nivolumab) = 23. Subjects in the Phase 1b portion will be included in the overall toxicity and efficacy analysis of the study. Subjects who are not evaluable will be replaced. Up to 28 patients may need to be registered (enrolled) in order to obtain the 23 evaluable patients.

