**5.9 Patient Replacement**

Subjects who are not evaluable will be replaced. Evaluable patients are those who receive at least 1 dose of HD IL2 and at least 1 dose of nivolumab.

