DLT evaluable patients: All patients who receive at least 1 dose of HD IL2 and at least 1 dose of Nivolumab will be evaluable for the primary endpoint of toxicity in the phase Ib portion of the trial. Subjects who are not evaluable will be replaced.

The phase II portion of the trial will be a Simon mini-max 2-stage design. The first stage will accrue 12 patients (including any response evaluable patients accrued in the phase 1b portion). If more than 2 patients have a response (CR or PR) out of the 12 patients, then we will accrue 11 more patients for a total sample size of 23 evaluable patients. If more than 8 responses (CR or PR) are observed in the 23 evaluable patients, then we will recommend further study of the combination. This design has 80% power and 10% type I error. If the true ORR of the combined treatment is 25% or less, the probability of early termination of the trial is 39%. If the true ORR is 46% or greater, then the probability of stopping early is only 3.6%. Patients accrued in the Phase Ib portion of the trial will also be included in the Phase II if they are evaluable as defined below.

Response Evaluable Patients: All patients who receive at least 1 dose of Nivolumab and IL-2 will be evaluable for the primary endpoint of overall response proportion in the phase II portion of the trial. If response at 12 weeks is not recorded for the patient, then the patient will be considered a non-responder.

We expect accrual to the entire study to be completed over a period of 24 months.

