## 11.2 Data Analyses Plans

Primary Endpoint Analysis:

Phase 1b: DLT count and proportion will be reported. Type, grade and attribution will be described by body system in the first 10 DLT evaluable patients. Number of IL-2 cycles and doses and Nivolumab doses will be summarized.

Phase II: Overall response rate at 12 weeks will be reported with the sample size and proportion of evaluable patients and the corresponding 95% exact binomial confidence interval.

Secondary Endpoint Analyses:

Safety will be defined by frequency of drug-related grade 3-5 adverse events including adverse events of interest within the duration of protocol, specified therapy and an additional 60 days following the last dose with the combination of HD IL2 and nivolumab, as assessed by NCI's CTCAE version 4.0. Counts and frequencies will be reported by body system, type and grade. Cycles and of each drug and doses/cycle of IL-2 will be described using descriptive statistics.

Survival endpoints are 24-month Overall Survival (OS) and 24-month Progression-Free Survival (PFS) as assessed by RECIST 1.1 criteria in subjects treated with the combination. Product-limit estimates from Kaplan-Meier methods will be used to report the 24-month OS and PFS proportions with 95% confidence intervals. Kaplan-Meier figures will be produced.

Interim Analysis for efficacy: An interim analysis for efficacy is planned after 12 response evaluable patients have been enrolled (total in the phase I b/II portions). If 2 or less patients have a response at 12 weeks then the trial will terminate. .

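### Section 7.1.1 requires re-evaluation before a patient counts as evaluable for response, while Section 11.1 counts every patient dosed with both drugs and scores a missing week-12 response as non-response

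*Combined protocol and SAP*

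**What the plan says.** Section 7.1.1 limits response evaluability, by the word *only*, to patients with measurable disease at baseline who received at least one dose of each drug "and have had their disease re-evaluated will be considered evaluable for response". Its one exception keeps patients with objective progression before the end of cycle 1.

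Section 11.1 sets no re-evaluation condition: "All patients who receive at least 1 dose of Nivolumab and IL-2 will be evaluable for the primary endpoint of overall response proportion". It adds a missing-data rule: "If response at 12 weeks is not recorded for the patient, then the patient will be considered a non-responder". The Statistical Methodology part of the synopsis gives the same definition and the same missing-data rule.

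Two further places define evaluability by dosing alone. The synopsis row on subject numbers has "Number of evaluable subjects (those who receive at least 1 dose of HD IL2 and at least 1 dose of nivolumab) = 23". Section 5.9, on replacement, has "Evaluable patients are those who receive at least 1 dose of HD IL2 and at least 1 dose of nivolumab".

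Section 11.2 uses two labels. For the interim look it says "An interim analysis for efficacy is planned after 12 response evaluable patients have been enrolled", which is the 11.1 term. For the Phase II primary analysis it says "Overall response rate at 12 weeks will be reported with the sample size and proportion of evaluable patients", without saying which definition of evaluable applies.

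**The concern.** Both rules cannot hold for a patient who received both drugs and was never re-evaluated. Under 11.1 that patient is a non-responder in the denominator. Under 7.1.1 the patient is left out. No text ranks the two or confines 7.1.1 to a supportive analysis.

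The schedule allows such patients. The first on-treatment scan is at week 12 (Sections 6.2.2 and 6.4). The end-of-treatment visit in 6.2.4 lists no imaging. Once all protocol therapy has stopped, Section 6.3 leaves scans to the investigator and standard of care. Someone who stops both drugs for toxicity before week 12 may therefore have no scan at all.

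At stake is the Phase II primary estimate and its confidence interval. A response cannot be recorded without re-evaluation, so 7.1.1 can remove only non-responders, and any shift is upward. With two definitions left standing, the choice between them could be made after the data are seen.

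**Working it through.** **1. The plan's own figures.** Inputs from Section 11.1: 12 patients in stage 1, continue if more than 2 respond; 23 in total, positive if more than 8 respond; response rates of 25% and 46%. Write b(x; n, p) for the binomial probability.

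- Early stopping: the sum of b(x; 12, p) for x = 0 to 2.
- Positive result: the sum over x = 3 to 12 of b(x; 12, p) × P(Bin(11, p) ≥ max(0, 9 − x)).

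| True rate | Early stopping | Positive result |
|---|---|---|
| 25% | 0.391 | 0.0944 (type I error) |
| 46% | 0.036 | 0.8012 (power) |

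These reproduce the stated 39%, 3.6%, 10% (as a ceiling) and 80%.

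**2. Who is affected.**

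| Patient dosed with both drugs | Section 7.1.1 | Section 11.1 |
|---|---|---|
| Re-evaluated at week 12 | in | in |
| Re-evaluated only at another time | in | in, week-12 response missing = non-responder |
| Objective progression before end of cycle 1 | in | in |
| Never re-evaluated, no documented objective progression | **out** | in, non-responder |

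The measurable-disease condition adds nothing, since 3.1.8 already makes it an entry criterion. Only the last row differs.

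**3. Effect on the reported rate.** Take 9 responders, the smallest positive result, and let k be the number of patients in the last row. The documents give no value for k, so 1 to 3 is assumed. The estimate is 9/(23 − k). The exact 95% limits for x of n are the 2.5% point of Beta(x, n − x + 1) and the 97.5% point of Beta(x + 1, n − x).

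| k | Estimate | Exact 95% CI | Shift (points) |
|---|---|---|---|
| 0 (11.1) | 9/23 = 39.1% | 19.7–61.5% | – |
| 1 | 9/22 = 40.9% | 20.7–63.6% | +1.8 |
| 2 | 9/21 = 42.9% | 21.8–66.0% | +3.7 |
| 3 | 9/20 = 45.0% | 23.1–68.5% | +5.9 |

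No response has been added in any row.

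**4. Effect on the decision.** The cutoffs are counts of responders, and the excluded patients contribute none. Section 5.9 replaces only patients who did not receive both drugs, so those never re-evaluated keep their places among the 12 and the 23. The type I error stays at 0.0944.

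It would change only if these patients were also replaced, which 5.9 does not allow. In that case, with a share m of dosed patients never re-evaluated (assumed), a true 25% among all dosed patients becomes 0.25/(1 − m) among those counted. The probability of a positive result is then 0.123 at m = 5% and 0.159 at m = 10%, and it passes 0.10 at about m = 1.1%.

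**The case against.** The strongest reply is that the plan already fixes the denominator. Section 11.1 is written for the Phase II primary endpoint and carries its own missing-data rule, which the synopsis repeats. Section 7.1.1 names neither that endpoint nor week 12. It sits in a general RECIST section, and its following sentence is about assigning response categories, which an unassessed patient cannot have. On that reading 7.1.1 says who can be classified, and 11.1 says how everyone else is counted. An analyst working within Section 11 would report x/23.

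The group is also small. Re-evaluation need not be imaging, since superficial lesions that cannot be imaged may be measured clinically. Standard-of-care scans can continue after treatment stops, and Section 7.1.4.3 asks for every effort to document progression after discontinuation. A shift of 1.8 to 5.9 points is modest against an interval about 42 points wide (61.5 − 19.7 = 41.8).

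Much of this stands. The intent is clear, the group is narrow, its size is unknown and the go/no-go decision is unaffected. The type I errors above 10% belong to a replacement rule the plan does not have and do not measure this defect. The classification reading does not succeed, though. Section 7.1.1 says that only re-evaluated patients are evaluable for response, which is a statement about the denominator, and the Phase II sentence in 11.2 does not point back to 11.1. A wide interval does not excuse a bias that can go only one way.

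**Conclusion.** The concern holds. Two incompatible definitions of the response denominator stand in the plan, and 7.1.1, if followed, would bias the primary response rate upward by dropping only non-responders. With 9 responders the shift is 1.8, 3.7 or 5.9 points for an assumed 1, 2 or 3 patients never re-evaluated. With three, the smallest positive result would read as 45.0%, close to the hypothesized 46%.

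The problem is confined to the reported estimate and its interval. The cutoffs, N = 23 and the type I error of 0.094 hold as long as 5.9 is applied as written. It should be fixed before analysis, but it does not undermine the design.

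**What to change.** 1. In Section 7.1.1, add that for the primary endpoint and the interim count the Response Evaluable definition in 11.1 applies: all patients with at least one dose of HD IL-2 and at least one dose of nivolumab, a missing week-12 response counted as non-response, and such patients not replaced.
2. In the Phase II sentence of Section 11.2, replace the bare term for evaluable patients with *response evaluable patients as defined in 11.1*.

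The cost is two wording changes, with no new analyses and no change to sample size, cutoffs or type I error. The reported rate may be slightly lower than it would be under 7.1.1.

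Power of 0.801 assumes that the hypothesized 46% already counts missing responses as non-responses. If 46% was meant for re-evaluated patients only, the rate among all dosed patients is 0.46(1 − m). For an assumed m of 5% or 10% that is 43.7% or 41.4%, with power 0.734 or 0.656. The plan already carries that cost, because 11.1 is its existing rule.
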